Administration Of Calcium Gluconate for The Reduction of Blood Loss During Elective Cesarean Delivery

INTRODUCTION

Postpartum hemorrhage (PPH) is the leading cause of death related to pregnancy, reported as 5% of all deliveries and assumed to be underestimated [1]. Known risk factors include uterine atony, genital tract trauma, retained placental tissue and more [2]. PPH can lead to blood transfusion, disseminated intravascular coagulation (DIC), hysterectomy, or death [2]The prophylactic administration of uterotonic agents as part of an active management of the third stage of labor has been proven to reduce rates of PPH [3]. However, even with these treatments, PPH rate is still relatively high, and puts women at risk of heavy bleeding and death. In addition, PPH is a risk factor for postpartum complications such as venous thromboembolic disease [4].

Calcium is a divalent cation found both intracellular and extracellular. It is a key component in the coagulation cascade and known as factor IV. It has a role in platelet activation, and it is an important co-factor for the activation of factors II and X [5]. K. M. Ho et al. had proven a concentration-dependent effect of hypocalcemia on in vitro clot strength in patients at risk of bleeding [6]. Calcium gluconate is the calcium salt of gluconic acid, and it has a relatively strong safety profile.

Hypocalcemia is a poor prognostic factor in actively bleeding patients. In trauma, the term "the trauma triad of death", describing the combination of hypothermia, acidosis, and coagulopathy as a vicious cycle that can lead to patient death eventually, has been changed to "the diamond of death" or "the lethal diamond", including hypocalcemia in the positive feedback loop of patient deterioration[7]–[9], emphasizing the need to monitor calcium levels when treating trauma patients with hemorrhagic shock. This mechanism doesn't apply only to trauma patients but to every patient that suffers from significant bleeding [10], [11]

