Calcium also has a positive inotropic effect both on skeletal muscle and smooth muscle. The inotropic effect doesn't skip the myometrium, and it is well-established that hypocalcemia can impair myometrial contractility [12], [13]. As so, calcium channel blockers are prescribed as a tocolytic drug and calcium gluconate should be considered as adjuvant therapy for treating PPH duo to atony, in case of prolonged tocolytic or magnesium sulfate use prior to delivery [14]. Studies have already shown an association between low ionized calcium levels and the risk for severe bleeding. In one study, the rate of hypocalcemia was 10.6% in patients with non-severe PPH and 51.5% in patients with severe PPH [15]. Furthermore, in a pilot randomized controlled trial of patients with risk factors for uterine atony, calcium was shown to reduce uterine atony compared to placebo [16]. However, current studies have small sample size and are limited to a high-risk population. Although it is acknowledged that hypocalcemia combined with acidosis and hypothermia contribute to worsening coagulopathy and increased morbidity in PPH [2], there are no recommendations in current guidelines for monitoring calcium levels or prescribing calcium as a prophylactic measure for the third stage of labor [15], despite atony and coagulopathy being significant causes of PPH.

Co-administration of calcium and oxytocin was examined in previous study, and there were no changes in maternal hemodynamics [17].

HYPOTHESIS

Administration of Calcium Gluconate at the third stage of elective Cesarean delivery will decrease the rates of blood loss during and after the surgery by reducing the rates of uterine atony and development of coagulopathy, thus has the potential of reducing the incidence of PPH and its complications without severe side effects.

RESEARCH QUESTIONS

Primary research question

Population (P), Intervention (I), Comparison (C), Outcome (O)

- P: All women undergoing elective cesarean delivery.
- I: Administration of Calcium Gluconate 10% IV following umbilical cord clamping.
- C: Administration of normal saline 0.9% IV following umbilical cord clamping.
- O: Decreased mean hemoglobin drop after cesarean delivery.

Outcome measures

Primary outcome:

.1 Decreased mean hemoglobin drop after cesarean delivery at the Calcium gluconate arm, compared to the control arm.

Secondary outcome:

- 1. The rate of women with a decrease of hemoglobin levels of 2 gr/dl or more.

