- 2. The need for additional therapy for the management of PPH
- 3. Receipt of blood products.
- 4. Patients treated with intravenous ferrous (iron).
- 5. The estimated blood loss during the surgery.
- 6. Hospitalization length of stay.
- 7. Duration of cesarean delivery.
- 8. A composite of adverse maternal outcomes including at least one of the following: admission to intensive care unit (NICU), the need for a surgical treatment for uncontrolled PPH, massive blood transfusion (defined as transfusion of ≥10 units red blood cells (RBCs) in 24 hours, disseminated intravascular coagulation (DIC), and death.
- 9. Endometritis or antibiotic treatment following CD.

PROPOSED TRIAL

Design: Multi Center (Rambam Health Care Campus, Soroka Medical Center), clusterrandomized, double-blind controlled trial.

Eligibility criteria for participants:

We plan to conduct a randomized control trial of all women undergoing elective cesarean delivery.

Inclusion criteria:

1. Gestational age of 35 weeks or more.

Exclusion criteria:

- 1. Age younger than 18 years old.
- 2. Patients treated with calcium channel blockers.
- 3. Chronic renal failure and hyperphosphatemia.
- 4. Sarcoidosis.
- 5. Hypocalcemia (ionized Ca<1 mmol/L) or hypercalcemia (ionized Ca> 1.3 mmol/L) before the surgery.
- 6. Any QT abnormalities as evident by ECG before Calcium Gluconate administrations or any known conduction abnormality.

Research arms and randomization:

After signing a consent form prior to the surgery (at the pre-operative assessment), At the third stage of labor, women who gave their consent to participate in the study will get either 10 ml of Calcium Gluconate 10% solution (containing 0.94 gr of calcium gluconate) diluted in 100 ml of normal saline IV or 110 ml of normal saline IV.

The solutions will be given in addition to Carbetocin (a long acting oxytocin analogue), in both arms.

We will use calcium gluconate during even-numbered months and normal saline during oddnumbered months, or vice versa, according to randomization that will be known to the primary researcher alone.

A blood sample will be drawn at the beginning of the surgery and sent for blood gas analysis, determining ionized calcium levels and coagulation profile. Women with hypocalcemia or hypercalcemia will be excluded from the trial. Only patients with normal calcium levels between 1.0-1.3 mmol/L will be included in this trial.

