An ECG strip will be done prior to the surgery, making sure that the patient doesn't suffer from a QT segment abnormality.

All patients will be monitored with a 3 lead- ECG prior, during, and 2 hours following calcium administration. Patients with QT interval abnormalities will be excluded from the trial.

After the surgery, a blood sample will be drawn and sent to blood gas analysis (determining ionized calcium levels) and for coagulation profile. A complete blood count will be routinely taken for all women the next day. The hemoglobin level will be compared to the hemoglobin level prior to CD.

ANALYSIS PLAN

Binyamin Y et al. demonstrated an average blood loss of 1.05 g/dL in 1000 women who have had a cesarean delivery for different indications[17]. Assuming a reduction in blood loss of 30% attributed to both coagulative effect and uterotonic effect of Calcium, and calculating a dropout rate of 10%, a sample size of 1180 patients (590 in each arm) is needed to achieve power of 0.8 and p-value <0.05. We will use SPSS 28 (IBM inc.) for statistical analysis. Categorical variables will be compared using the chi-square test or fisher's exact test. Continuous variables will be compared using the student's t-test or Mann-Whiteny test. After testing for collinearity, confoundment and interaction, a multivariate model will be built to assess the effect of calcium supplementation on postpartum hemorrhage. Alpha < 0.05 is considered statistically significant.

References:

- C. Deneux-Tharaux, M.-P. Bonnet, and J. Tort, "[Epidemiology of post-partum haemorrhage].," J Gynecol Obstet Biol Reprod (Paris), vol. 43, no. 10, pp. 936–50, Dec. 2014, doi: 10.1016/j.jgyn.2014.09.023.
- [2] "Postpartum Hemorrhage ACOG PRACTICE BULLET IN Clinical Management Guidelines for Obstetrician-Gynecologists," 2017. [Online]. Available: http://www1.health.nsw.gov.au/pds/ActivePDSDocuments/
- [3] L. Sentilhes, F. Goffinet, C. Vayssière, and C. Deneux-Tharaux, "Comparison of postpartum haemorrhage guidelines: discrepancies underline our lack of knowledge," *BJOG*, vol. 124, no. 5, pp. 718–722, Apr. 2017, doi: 10.1111/1471-0528.14305.
- [4] L. Thurn, A. Wikman, and P. G. Lindqvist, "Postpartum blood transfusion and hemorrhage as independent risk factors for venous thromboembolism," *Thromb Res*, vol. 165, pp. 54–60, May 2018, doi: 10.1016/j.thromres.2018.03.002.

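### The next-day haemoglobin is used as measured for every woman, transfused or not, so red cells given before that count can hide part of a heavy bleeder's drop and modestly pull both haemoglobin outcomes toward the null

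*Protocol*

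**What the plan says.** The primary outcome (Protocol, Outcome measures) is "Decreased mean hemoglobin drop after cesarean delivery at the Calcium gluconate arm, compared to the control arm". Secondary outcome 1 is "The rate of women with a decrease of hemoglobin levels of 2 gr/dl or more".

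The end of the section on research arms and randomization says how the drop is obtained: "A complete blood count will be routinely taken for all women the next day", and then "The hemoglobin level will be compared to the hemoglobin level prior to CD". The other post-operative sample is for ionized calcium and coagulation, not for the haemoglobin outcome.

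Transfusion is foreseen. Secondary outcome 3 is "Receipt of blood products", and massive transfusion is a component of the composite in secondary outcome 8. The Analysis plan compares continuous variables by t-test or Mann-Whitney and categorical ones by chi-square or Fisher's exact test. Nothing in the protocol gives a transfused woman a different haemoglobin value, a different classification or a sensitivity analysis.

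**The concern.** Both haemoglobin outcomes stand in for blood loss. Red cells given between surgery and the next-day count raise that count, so the recorded drop is smaller than the drop caused by bleeding. The women affected are those whose bleeding the trial most wants to measure. One of them can be recorded as not reaching a 2 g/dl drop.

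The trial's hypothesis is that calcium reduces bleeding. If that is true, fewer women on calcium cross whatever threshold leads to transfusion, more control women have their drops masked, and the contrast between arms is understated. At stake are some loss of effect size on the primary outcome and a possible loss of contrast on the 2 g/dl outcome.

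**Working it through.** **Inputs from the protocol.** Control mean drop 1.05 g/dL ("demonstrated an average blood loss of 1.05 g/dL in 1000 women"); 30% reduction and 10% dropout; 590 per arm; power 0.80; alpha 0.05, taken as two-sided because sidedness is not stated.

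- Planned difference: 0.30 × 1.05 = 0.315 g/dL, so the calcium mean is 0.735 g/dL.
- Evaluable per arm: 590 × 0.90 = 531.

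**The plan's own figure.** No SD is given, so 590 per arm cannot be reproduced, only back-solved: SD = 0.315/(1.960 + 0.8416) × √(531/2) = 1.83 g/dL. For comparison, SD 1.0 would need 159 evaluable per arm, or 177 with dropout. Both SDs are carried forward.

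**Assumptions, none of them in the protocol.** Drops are normal. The heaviest-bleeding 1-5% of controls receive red cells before the next-day count. The same threshold t applies in both arms. Transfusion raises haemoglobin by r = 1 or 2 g/dL. The upper end of 5% is borrowed from the Introduction's figure for postpartum haemorrhage ("reported as 5% of all deliveries and assumed to be underestimated"), which is not a transfusion rate.

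**Formulas.**
- Transfused share, control: p_C; threshold t = 1.05 + SD × z(1 − p_C).
- Transfused share, calcium: p_T = 1 − Φ((t − 0.735)/SD).
- Observed difference: D = 0.315 − r × (p_C − p_T).
- Power = Φ(D/(s × √(2/531)) − 1.96), where s is the SD after masking. Masking trims the upper tail, so s is below the original SD.

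**Primary outcome.**

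| SD | p_C | p_T | r | D | shrinkage | s | power |
|---|---|---|---|---|---|---|---|
| 1.83 | 1% | 0.6% | 1 | 0.311 | 1.2% | 1.81 | 0.80 |
| 1.83 | 2% | 1.3% | 2 | 0.301 | 4.4% | 1.77 | 0.79 |
| 1.83 | 5% | 3.5% | 2 | 0.284 | 9.8% | 1.69 | 0.78 |
| 1.0 | 1% | 0.4% | 1 | 0.309 | 1.9% | 0.98 | 0.999 |
| 1.0 | 2% | 0.9% | 2 | 0.293 | 7.0% | 0.96 | 0.999 |
| 1.0 | 5% | 2.5% | 2 | 0.265 | 15.9% | 0.91 | 0.997 |

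Worked line (SD 1.83, 5%, r = 2): t = 1.05 + 1.645 × 1.83 = 4.06; p_T = 1 − Φ(3.325/1.83) = 0.0346; D = 0.315 − 2 × (0.0500 − 0.0346) = 0.284.

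If p_T = p_C, then D = 0.315 and nothing is lost.

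**The 2 g/dl outcome.** A woman changes category only if t − r falls below 2.

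- SD 1.83: true rates 30.2% and 24.5%, difference 5.7 points. Even at 5% transfused and r = 2, t − r = 2.06, so nobody crosses and the difference stays at 5.7.
- SD 1.0: true rates 17.1% and 10.3%, difference 6.8 points. With drops above 3 g/dL transfused (2.6% and 1.2%) and r = 2, the rates become 14.7% and 9.2%, a difference of 5.5 points. At 5% transfused and r = 2 they become 12.3% and 7.9% (4.4 points after rounding the unrounded difference). With r = 1, nobody crosses at 1-2% transfused; at 5% the difference falls to 5.7 points.

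**The case against.** The strongest reply is that the quoted sentence only describes sampling, and that handling a post-randomisation event such as transfusion belongs in a statistical analysis plan, which may exist but is not shown. This stands only in part. The protocol names the time point, the comparison value and the population, so it fixes how the drop is formed. Following it as written understates the drop of a woman given red cells before the count. A later document could add a rule, and that is the natural place for the details.

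Four further points stand as limits:

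- **As-measured haemoglobin is a legitimate treatment-policy outcome.** If calcium has no effect on bleeding, there is no differential masking, so this mechanism does not inflate type I error. For this reason the primary analysis need not be replaced.
- **The planning value may already include transfused women.** The documents do not say whether they were excluded or corrected in the source of the 1.05 g/dL. If they were included as measured, deducting masking from 0.315 partly counts it twice.
- **Timing is unknown.** Only red cells given before the next-day count matter, and secondary outcome 3 covers blood products in general.
- **No single SD used here harms both outcomes materially.** At SD 1.83 the 2 g/dl outcome does not move; at SD 1.0 the primary has power to spare.

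A reader might infer that power falls to about 0.65. That figure pairs 5% of controls transfused with half as many on calcium, a 2 g/dL rise and an SD held at 1.83. At that SD, a 0.315 g/dL shift past a common threshold gives 5.0% against 3.5%, not 2.5%, and masking also lowers the SD; power is then 0.78. A reader might also infer that a benefit among severe bleeders would show only in the transfusion count. The protocol also collects additional therapy for haemorrhage, intravenous iron, estimated blood loss and the adverse-outcome composite.

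**Conclusion.** The point holds as a moderate weakness, not a fatal one. The stated rule understates the drop of women given red cells before the next-day count. If calcium reduces bleeding, that biases both haemoglobin outcomes toward the null.

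Under the assumptions above, the loss on the primary is about 1-10% of 0.315 g/dL at the back-solved SD and about 2-16% at SD 1.0, with little effect on power in either case. The 2 g/dl outcome is more exposed, but only if the SD is near 1.0 and transfusion lifts women back below the cut-off. The documents do not support a claim that the trial is substantially underpowered for this reason, or that the bias is certain to occur.

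**What to change.** 1. **Secondary outcome 1.** Count any woman given red cells before the next-day count as having a drop of 2 g/dl or more. Report the as-measured version as a sensitivity analysis.
2. **Primary outcome.** Keep the as-measured comparison. Before unblinding, pre-specify a sensitivity analysis that uses the last haemoglobin before the first red-cell unit where one exists. Where none exists, give transfused women the worst rank in the Mann-Whitney test that the Analysis plan already names.

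The cost is a few sentences in the protocol or statistical analysis plan, plus the time of red-cell transfusion from the chart. Receipt of blood products is already an outcome. There is a small downside: a woman transfused because her haemoglobin was low at baseline may be counted as reaching the 2 g/dl drop, and the as-measured version will show how much this matters. A pre-transfusion value is also taken at a different time from the next-day count, which is one reason to use it only as a sensitivity analysis. Neither transfusion practice nor blood sampling has to change.

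### The stated pooled tests carry no hospital term, although two hospitals are combined and allocation by calendar month does not balance hospital between the arms

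*Protocol*

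**What the plan says.** Under Proposed Trial the design is given as "Multi Center (Rambam Health Care Campus, Soroka Medical Center), clusterrandomized, double-blind controlled trial". Under Research arms and randomization the arm follows the calendar: "We will use calcium gluconate during even-numbered months and normal saline during oddnumbered months, or vice versa, according to randomization". The text does not say whether one schedule covers both hospitals or each has its own, nor whether the hospitals start and stop together.

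The primary outcome is "Decreased mean hemoglobin drop after cesarean delivery at the Calcium gluconate arm, compared to the control arm". The secondary outcomes include several that local practice may influence: "Patients treated with intravenous ferrous (iron"), length of stay, duration of surgery, additional therapy and blood products.

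The Analysis Plan fixes the tests in two sentences: "Categorical variables will be compared using the chi-square test or fisher's exact test" and "Continuous variables will be compared using the student's t-test or Mann-Whiteny test". It then adds one adjusted analysis: "After testing for collinearity, confoundment and interaction, a multivariate model will be built to assess the effect of calcium supplementation on postpartum hemorrhage". Hospital is not mentioned in any of the three sentences.

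**The concern.** Alternating months put women from both hospitals into both arms, but nothing holds each hospital's share equal between the arms. The shares drift apart if the hospitals' relative volumes differ between even and odd months, or if one hospital contributes more months of one kind than of the other. A pooled t-test or chi-square test reads the resulting hospital contrast as part of the treatment contrast.

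This is separate from month-level clustering. A clustering correction widens the interval to allow for month-to-month variation. It does not remove a realised imbalance in a known two-level factor, whereas a hospital term does. At stake are mainly the secondary outcomes that may follow local policy, where hospitals could differ for reasons unrelated to calcium.

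**Working it through.** **Inputs from the protocol (Analysis Plan).** Control mean drop 1.05 g/dL; assumed reduction 30%; 590 women per arm; 10% dropout; power 0.8; alpha 0.05 (taken as two-sided).

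- Planned effect: 0.30 × 1.05 = 0.315 g/dL.
- Evaluable per arm: 590 × 0.9 = 531.
- No SD is stated, so the sample size cannot be reproduced directly. The SD it implies is 0.315 × √(531/2) / (1.960 + 0.842) = 1.83 g/dL. I use 1.83, with 1.0 as a smaller alternative.

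**Inputs not in the protocol (assumptions).** Hospital shares and hospital differences in any outcome.

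**Formula.** Bias of the unadjusted difference = (share of hospital B in the calcium arm − its share in the saline arm) × (hospital difference in the outcome).

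**How large might the mix difference be?**

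- Two equal hospitals, 12 months, 1180 women, independent monthly volumes with a CV of 25%: by simulation the mix difference has an SD of 5.9 points, with 95% of trials within about 11.5 points. At a CV of 15% the SD is 4.2.
- Individual randomization without stratification gives an SD of 2.9 points, and a pooled test already allows for that much.
- If the two hospitals' monthly volumes correlate at 0.5, the SD falls to 4.6; at 0.8, to 3.7.
- Illustration: hospital A gives 295 women to each arm, and B gives 354 to calcium and 236 to saline (three months against two). Then 354/649 − 236/531 = 54.5% − 44.4% = 10.1 points.

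**Primary outcome, fixed mix difference (531 per arm).**

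| Mix difference | Hospital difference (g/dL) | Bias (g/dL) | Share of 0.315 | Type I error, SD 1.83 | Type I error, SD 1.0 |
|---|---|---|---|---|---|
| 5 points | 0.2 | 0.010 | 3% | 0.051 | 0.053 |
| 10 points | 0.2 | 0.020 | 6% | 0.054 | 0.062 |
| 10 points | 0.5 | 0.050 | 16% | 0.073 | 0.129 |
| 20 points | 0.5 | 0.100 | 32% | 0.145 | 0.371 |

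Averaged over a mix SD of 5.9 points, the type I error with SD 1.83 is 5.1 to 5.7% for hospital differences of 0.2 to 0.5 g/dL. With SD 1.0 and 0.5 g/dL it is about 7.2%.

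**Secondary outcomes, fixed mix difference (590 per arm).** False-positive rate = Φ(−1.96 + b/SE) + Φ(−1.96 − b/SE).

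- Intravenous iron 10% v 40% by hospital: pooled rate 25%, SE = √(2 × 0.25 × 0.75/590) = 0.0252. At 10 points b = 0.03 and the rate is 22%; at 5 points, 9%.
- Stay differing by 1 day (within-hospital SD 1 day): total variance 1 + 0.25 = 1.25, SE = √(2 × 1.25/590) = 0.0651. At 10 points b = 0.1 and the rate is 34%; at 5 points, 12%.
- Iron 20% v 30%: at 10 points b = 0.01 and the rate is about 7%.

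**Secondary outcomes, averaged over a mix SD of 5.9 points.** The pooled test assumes variance SE². The true variance is (0.059 × hospital difference)² + 2 × within-hospital variance/590. The rate is 2Φ(−1.96 × SE/√true variance).

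- Iron 10% v 40%: within-hospital variance (0.09 + 0.24)/2 = 0.165. True variance 0.000313 + 0.000559 = 0.000873, against SE² = 0.000636. Rate about 9%.
- Stay: true variance 0.00348 + 0.00339 = 0.00687, against SE² = 0.00424. Rate about 12%.
- Iron 20% v 30%: within-hospital variance (0.16 + 0.21)/2 = 0.185, and the same formula gives about 5.5%.
- With volume correlation 0.5 (SD 4.6 points), the first two fall to about 7% and 9%.

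**The case against.** **The multivariate model could contain hospital.** This stands in part. A reader might infer that no planned analysis can include hospital, and the protocol does not support that: the covariates are unnamed, and hospital could survive the confounding tests. But the model's outcome is postpartum hemorrhage, and hospital would enter only if those tests on the data selected it. It gives no hospital term for the hemoglobin drop, intravenous iron, length of stay or duration of surgery.

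**Strata and covariates usually belong in an SAP, which is not shown.** Silence alone would indeed be no finding. Here, though, the protocol commits to particular unadjusted tests for a design in which it has itself introduced two hospitals, and a hospital-stratified analysis would differ from those tests.

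**The imbalance is hypothetical.** This stands. Nothing in the protocol says that the mix will differ. A late start, an odd number of months or a large practice difference between the hospitals are all assumptions. If both hospitals alternate throughout with similar relative volumes, the bias is near zero.

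**The largest error rates describe a bad draw.** This stands too. A reader might take 22% and 34% as the trial's expected false-positive rates. They hold only given a 10-point mix difference together with large hospital differences. With a mix SD of 5.9 points, a difference that large occurs about 9% of the time; with volume correlation 0.5, about 3%.

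**Month clustering is the larger matter.** Agreed. A reader might infer that a hospital term repairs the allocation by month. It does not: it leaves month-to-month variation untouched.

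**Conclusion.** The point holds as an avoidable weakness in the stated tests, not as a demonstrated bias. The named comparisons omit a design factor that month allocation does not balance, and the only adjusted model does not reach the primary outcome or most of the secondary ones.

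For the primary outcome the consequence is small across plausible ranges, and it becomes material only if a large imbalance meets a large hospital difference. For practice-driven secondary outcomes the averaged false-positive rate of about 9 to 12% rests on equal hospitals, 12 months, independent monthly volumes with a CV of 25%, and large hospital differences. Milder values bring it close to the nominal 5%. The case for change therefore rests less on the size of the risk than on its being removable at almost no cost.

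**What to change.** In the Analysis Plan, replace the pooled tests with hospital-adjusted comparisons:

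- Hemoglobin drop and other continuous outcomes: a linear model with arm, and hospital as a fixed effect.
- Binary outcomes: a hospital-stratified (Mantel-Haenszel) comparison, or a model with a hospital term.
- All of these: combined with a method that accounts for the hospital-month clusters, because the hospital term alone does not.
- Baseline table: each arm's composition by hospital.

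It would also help to state whether the month schedule is drawn once or per hospital.

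Cost: a short rewording and one extra parameter per model. Each woman's hospital is known from where she delivers, so no extra patients, data or procedures are needed. Fixing it before the data are seen also prevents a later choice between adjusted and unadjusted results.

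### Treatment is allocated by alternating calendar month, but the named tests treat women as independently randomised, so the 5% error rate is not held if outcomes vary irregularly by month

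*Protocol*

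**What the plan says.** Under Proposed Trial, the design line calls this a "clusterrandomized, double-blind controlled trial" at two centres. Under Research arms and randomization, allocation works as follows: "We will use calcium gluconate during even-numbered months and normal saline during oddnumbered months, or vice versa, according to randomization". No woman is randomised individually. The text does not say whether one draw fixes the schedule for both centres.

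The primary outcome (Outcome measures) is "Decreased mean hemoglobin drop after cesarean delivery at the Calcium gluconate arm, compared to the control arm".

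The Analysis Plan then fixes the tests: "Continuous variables will be compared using the student's t-test or Mann-Whiteny test", and "Categorical variables will be compared using the chi-square test or fisher's exact test". It adds that "a multivariate model will be built to assess the effect of calcium supplementation on postpartum hemorrhage", without giving the form of that model. The significance rule is "Alpha < 0.05 is considered statistically significant". On size it says that "a sample size of 1180 patients (590 in each arm) is needed to achieve power of 0.8", after a 10% dropout allowance and an assumed 30% reduction from 1.05 g/dL. That section contains no term for month, centre or cluster, and no ICC, cluster size or design effect.

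**The concern.** All four named tests estimate the standard error from the spread among women, as if each had been allocated separately. Here every woman operated on in a given month at a given centre receives the same infusion. Anything that moves outcomes irregularly from one month to the next (staff rotation, case mix, laboratory or transfusion practice) therefore goes into the arm difference, while the standard error takes no proper account of it. If the month-level ICC is above zero, confidence intervals are too narrow, and a nominally significant primary result could be ordinary month-to-month variation. The same applies to every secondary outcome analysed with these tests.

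The cause is specifically irregular month variation. Stable centre differences and a smooth season are largely balanced by alternation and do not inflate the error.

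**Working it through.** **Inputs from the protocol.** 1180 women, 10% dropout, so 1180 × 0.9 = 1062 evaluable (531 per arm). Difference 0.30 × 1.05 = 0.315 g/dL. Alpha 0.05, taken as two-sided. Power 0.8. Two centres.

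**Assumptions, because the protocol gives no figure.** Centres of equal size, one even/odd schedule at both, 12 or 24 months, ICC from 0 to 0.05. The value 0.05 is an upper sensitivity case.

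**Step 1: the stated sample size.** No SD is given, so 1180 cannot be reproduced directly. Solving backwards from the ordinary two-sample formula:

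SD = 0.315 / [(1.960 + 0.842) × √(2/531)] = 1.83 g/dL.

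Putting 1.83 back gives 530 per arm, 589 after dividing by 0.9, and 1178 in total. The stated figure thus fits an individually randomised formula with no design effect, if the SD is about 1.83.

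**Step 2: true error of the planned t-test.** With m women per cluster, the design effect is DE = 1 + (m − 1) × ICC, and the error is approximately 2 × [1 − Φ(1.96/√DE)].

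- Month effects independent between centres, 12 months: 24 clusters, m = 1062/24 = 44.25. At ICC 0.01, DE = 1 + 43.25 × 0.01 = 1.43 and the error is 10.2%.
- Month effects shared by both centres, 12 months: 12 clusters, m = 88.5. At ICC 0.01, DE = 1 + 87.5 × 0.01 = 1.875 and the error is 15.2%.

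| ICC | 12 months, independent | 12 months, shared | 24 months, independent | 24 months, shared |
|---|---|---|---|---|
| 0 | 5% | 5% | 5% | 5% |
| 0.001 | 5.5% | 6.0% | 5.2% | 5.5% |
| 0.01 | 10.2% | 15.2% | 7.5% | 10.2% |
| 0.02 | 15.1% | 23.7% | 10.0% | 15.1% |
| 0.05 | 27.0% | 39.8% | 17.2% | 27.0% |

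Simulation (20,000 replicates per setting) agrees to within one percentage point. The chi-square test behaves the same way: with an assumed 15% risk, 12 months and ICC 0.01, its simulated error was 10.4% (independent) and 14.6% (shared). Outcomes rarer than 2%, as the composite may be, were not simulated.

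**Step 3: what does not cause it.** In simulation, a 0.3 SD centre difference alone left the t-test at 4.8%, and a 0.2 SD seasonal curve alone left it at 4.7%. A 12-month sine curve cancels exactly between even and odd months.

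**Step 4: an analysis at the level of allocation.** A test on calendar-month means held 4.6% to 5.3% in the settings of the table. Under a seasonal curve, month means without time terms become very conservative (0.1%); adding linear and annual sine/cosine terms restores 4.9% to 5.1%.

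**Step 5: power of that analysis at 1062 women.** With shared month effects, the non-centrality is 0.315 / [SD × √(4 × DE/1062)], on (months − 2) degrees of freedom. With SD 1.83 this is 2.80/√DE.

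| ICC | 12 months | 24 months |
|---|---|---|
| 0 | 0.71 | 0.76 |
| 0.001 | 0.68 | 0.75 |
| 0.01 | 0.46 | 0.61 |
| 0.02 | 0.33 | 0.50 |
| 0.05 | 0.19 | 0.33 |

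If the SD were 1.0 g/dL, power would be about 0.80 or more up to ICC 0.02, over 12 or 24 months.

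**The case against.** The strongest reply is that the harm is conditional. The inflated figures rest on assumed ICCs, and there are reasons to expect a small one: elective surgery only, the same uterotonic in both arms, a restricted calcium range, and a within-woman change as outcome. At ICC 0.001 the error is 5% to 6%, and nothing in the document supports 0.05. This stands as a limit on the size of the problem. It does not show that the ICC is negligible, and the protocol offers no figure that would.

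Second, the schedule matters. If the centres ran opposite even/odd schedules and shared the same month effects, those effects would cancel; a simulation of that case gave 4.8% to 5.2%. This also stands. But the allocation sentence reads most naturally as one schedule, and if month effects are independent between centres, opposite schedules give no protection (about 27% at ICC 0.05 over 12 months).

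Third, the loss of power rests on a back-solved SD, and the fall to 0.71 at ICC 0 is purely the cost of having few months. That is fair, so power is the secondary issue here.

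Fourth, the choice among cluster methods could be left to a statistical analysis plan that is not shown. The choice of method could be, but the mismatch could not: the protocol positively names tests that do not fit its declared design. A plan that followed them would repeat the error, and one that departed from them would contradict the protocol.

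**Conclusion.** The concern holds. The named tests do not match the stated unit of allocation, and the only model mentioned addresses a different outcome. The mismatch is certain from the text; its size is not. Under one schedule, the nominal 5% becomes roughly 7% to 15% at an assumed ICC of 0.01 over 12 to 24 months, more at higher ICCs, and stays at 5% if months do not differ. This should be corrected before any unblinded analysis, because it affects the primary p-value and every secondary comparison made with these tests.

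One limit remains under any analysis. A single even/odd choice allows only two allocation sequences (four if drawn separately by centre), so valid inference has to rest on modelling the month effects as exchangeable once smooth time trends are accounted for.

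**What to change.** Replace the patient-level tests with an analysis at the level of allocation.

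- **Primary outcome:** a linear mixed model for hemoglobin drop with arm and centre as fixed effects, a smooth calendar-time trend, random effects for month and for centre within month, and a small-sample degrees-of-freedom correction. Under a shared schedule, do not use month indicators, because they are collinear with arm. The error rate of this model was not itself simulated; the checks above are on month means.
- **Simpler alternative under a shared schedule:** regress calendar-month means (the average of the two centre means) on arm and the smooth time terms, with degrees of freedom from the number of months. This cannot be fitted if the centres run opposite schedules.
- **Centre-month means:** use them only if the schedules are separate and month effects can be taken as independent between centres, and then adjust for centre. With shared effects over 12 months, an unadjusted test on centre-month means still had an error of 8.7% at ICC 0.01.
- **Binary outcomes:** a mixed logistic model or GEE clustered on month, with a small-sample correction, or month-level proportions.
- **State in the protocol** whether both centres follow one schedule, and restate the power of 1180 women with the SD, ICC and number of months assumed.

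**Cost.** No new data are needed beyond date and centre of surgery, but this is more than a change of wording. Confidence intervals widen, and if the SD is near 1.83 g/dL power falls below 0.8, so more months or more women may be needed. With few months, each time term also costs degrees of freedom: over 12 months at ICC 0, simulated power falls from 0.71 to 0.64 once linear and annual terms are added.
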